7.6.3. Secondary Analyses

All secondary and exploratory endpoints will be summarized by study visit (if applicable) and treatment group using appropriate descriptive statistics.

7.6.3.1. Key Secondary Endpoint 1: Mean Change from baseline to Day 57 for FFI Pain and Difficulty combined score between EN3835 and placebo

The 1st key secondary estimand is defined by the following:

- **The *secondary clinical question of interest* is:** In participants with plantar fibromatosis, what is the difference in mean change from Baseline (Day 1) to Day 57 in foot pain and difficulty combined score (as measured with total combined score of the FFI pain subscale and the FFI difficulty subscale) between EN3835 and placebo, regardless of discontinuation of study intervention?
- **Treatment condition:** Randomized study intervention (EN3835 or placebo)
- **Target Population:** Adult participants with plantar fibromatosis who are included in the ITT Population.
- **Variable (Endpoint) of interest:** Mean change from Baseline (Day 1) to Day 57 in foot pain and difficulty combined score.
- **Treatments being compared:** The change from Baseline (Day 1) to Day 57 in the Total Combined (Pain and Difficulty) Subscale Score will be compared between EN3835 and placebo.

- **Intercurrent Event:** The treatment policy strategy will be adopted for the analyses.
 - Any new or change in concomitant treatment will not be adjusted for primary analyses.
 - Early discontinuation from the study is the potential intercurrent event that could occur. If participants do not have FFI Total Combined (Pain and Difficulty) subscale score at Day 57 due to early discontinuation, the missing values will be imputed before the analyses using a multiple imputation washout model. In multiple imputation washout model, all participants who are randomized and have a baseline assessment will be considered (Section 7.6.1.2 for more details on imputation).
- **Population Level-Summary measure:** Least square mean (LSM) estimate for treatment difference between EN3835 and placebo.
- **Method of Analyses:** The change from Baseline (Day 1) to Day 57 in Total Combined (Pain and Difficulty) subscale score will be calculated after the missing data imputation has been performed and will be analyzed using ANCOVA model on each multiply imputed dataset. The model will include the fixed effect of treatment group and FFI pain and difficulty subscale combined score at baseline, the maximum of Nodule length/Nodule width, and the total number of nodules as covariates. Treatment effects from these ANCOVA analyses will then be combined using Rubin's Method via the SAS PROC MIANALYZE procedure. The LSM estimate for each treatment, the LSM of treatment difference, their corresponding 95% confidence interval (CI) and associated p-value will be provided. Refer Section 7.6.1.2 for more details on this analyses.
- **Sensitivity analyses to secondary endpoint:** The following sensitivity analyses will be performed on secondary efficacy endpoint to assess the impact of missing data:
 - A sensitivity analyses will be performed based all observed data up to Day 57. The change from Baseline (Day 1) to Day 57 will be analyzed using an MMRM (Section 7.6.1.3).
 - Another sensitivity analyses will be performed using MMRM with imputation of missing values for participant who discontinue treatment or who are withdrawn from the study. The imputed missing values will be adjusted using TPA (Section 7.6.2).
- **Supportive analyses to secondary endpoint:** The secondary efficacy endpoint will also be analyzed using ANCOVA by FAS and mITT population.

The descriptive statistics for observed and change from baseline at each visit of the Total Combined (Pain and Difficulty) subscale score by treatment group will be provided.

The mean change from Baseline in the Total Combined (Pain and Difficulty) subscale score with observed data by treatment group will be presented using a line graph with error bars depicting the SE (on the y-axis) and visit along the x-axis using ITT, FAS and mITT population.

7.6.3.2. Key Secondary Endpoint 2: Clinician Global Impression of Change Scale

7.6.3.2.1. Key Secondary Endpoint 2: Primary Analyses

The 2nd key secondary estimand is defined by the following:

- **The *secondary* clinical question of interest is:** In participants with plantar fibromatosis, what is the difference in the proportion of EN3835-treated participants and those receiving only placebo reporting “Minimally Improved” (+1) “Much Improved” (+2) or “Very Much Improved” (+3) on CGIC, a 7-point scale ranging from –3 (“Very Much Worse”) to +3 (“Very Much Improvement”) at Day 57 between EN3835 and placebo, regardless of discontinuation of study intervention?
- **Treatment condition:** Randomized study intervention (EN3835 or placebo)
- **Target Population:** Adult participants with plantar fibromatosis who are included in the ITT Population.
- **Variable (Endpoint) of interest:** Difference in the proportion of participants reporting a response on the CGIC, a 7-point scale ranging from –3 (“Very Much Worse”) to +3 (“Very Much Improvement”) at Day 57
- **Treatments being compared:** The difference in proportion of participants reporting a response on the CGIC at Day 57 will be compared between EN3835 and placebo.
- **Intercurrent Event:** The treatment policy strategy will be adopted for the analyses.
 - Any new or change in concomitant treatment will not be adjusted for primary analyses.
 - Early withdrawal from the study is the potential intercurrent event that could occur. All participants who withdraw early from the study will be considered as non-responders. The responder is defined as a participant who reports a score to be “Minimal Improvement”, “Much Improvement” or “Very Much Improvement” on the CGIC at Day 57.
- **Population Level-Summary measure:** The stratum adjusted risk difference, associated 95% CI and p-value will be presented.
- **Method of Analyses:** The difference in proportion of responders between EN3835 and placebo will be analyzed using Cochran-Mantel-Haenszel (CMH) test stratified by total number of nodules at baseline. The stratum adjusted risk difference, associated 95% CI and p-value will be presented using CMH test. The frequency and percentage of responders and 95% CI will be provided based on the Wilson (Score) by treatment group.
- **Sensitivity analyses to secondary endpoint:** Sensitivity analyses will be performed using CMH with imputation of missing values for participant who discontinue treatment or discontinue/withdrawn from the study. The imputed missing values will be adjusted using TPA (Section 7.6.3.2.2).
- **Supportive analyses to secondary endpoint:** The secondary efficacy endpoint will also be analyzed using FAS and mITT population.

The degree of improvement in the 7-point scale as determined by the Investigator using CGIC Scale will be summarized using frequency and percentages with mean and SD by each treatment group and visit (ie, Days 15, 29, 43, and 57) for each foot.

A listing of CGIC Scale ratings by participant will be provided.

7.6.3.2.2. Sensitivity Analyses using CMH using Tipping Point Analyses (TPA)

The sensitivity analyses will be performed to assess the impact of missing data with CMH using delta adjustment for TPA as described in Section 7.6.3.2.2. The following 3 steps will be performed to impute the missing data based on Section 6.3.1 for sensitivity analyses:

[REDACTED]

The tipping point can be identified when the result is no longer statistically significant.

Shift parameters will begin with active-only adjustment, followed by a control adjustment that is half of the active adjustment, followed by all arms with identical shift adjustments, as stated in Step 2.

All steps above are repeated with different values of the shift parameter until the tipping point is reached or all possible values are explored. The tipping point can be identified when the result is no longer statistically significant (one p-value >0.025). It is possible a tipping point is not reached if little to no data is missing.

7.6.3.3. Key Secondary Endpoint 3: Difference of Mean Changes from Baseline to Day 57 for Nodular Hardness Measurements between EN3835 and Placebo

7.6.3.3.1. Participant Level Analyses:

The 3rd key secondary estimand is defined by the following:

- **The *secondary clinical question of interest* is:** In participants with plantar fibromatosis, what is the difference in mean change from Baseline (Day 1) to Day 57 in nodular hardness measurements (as measured by durometer) between EN3835 and placebo, regardless of discontinuation of study intervention?
- **Treatment condition:** Randomized study intervention (EN3835 or placebo)
- **Target Population:** Adult participants with plantar fibromatosis who are included in the ITT Population.
- **Variable (Endpoint) of interest:** Mean change from Baseline (Day 1) to Day 57 in Nodular Hardness.
- **Treatments being compared:** The mean change from Baseline (Day 1) to Day 57 in Nodular Hardness measurements will be compared between EN3835 and placebo.
- **Intercurrent Event:** The treatment policy strategy will be adopted for the analyses.
 - Any new or change in concomitant treatment will not be adjusted for primary analyses.
 - Early withdrawal from the study is the potential intercurrent event that could occur. If participants do not have nodular hardness at Day 57 due to early withdrawal, the missing values will be imputed before the analyses using a multiple imputation washout model. In multiple imputation washout model, all participants who are randomized and have a baseline assessment will be considered (Section 7.6.1.2 for details on imputation).
- **Population Level-Summary measure:** Least square mean (LSM) estimate for treatment difference between EN3835 and placebo.
- **Method of Analyses:** The change from baseline (Day 1) to Day 57 in nodular hardness will be calculated after the missing data imputation has been performed and will be analyzed using ANCOVA model on each imputed dataset. The model will

include the fixed effect of treatment group and average nodular hardness at baseline, the maximum of Nodule length/Nodule width, and the total number of nodules as covariates. Treatment effects from these ANCOVA analyses will then be combined using Rubin's Method via the SAS PROC MIANALYZE procedure. The LSM estimate for each treatment, the LSM of treatment difference, their corresponding 95% confidence interval (CI) and associated p-value will be provided (Section 7.6.1.2 for more details on this analyses).

- **Sensitivity analyses to secondary endpoint:** Following sensitivity analyses will be performed on secondary efficacy endpoint to assess the impact of missing data:
 - A sensitivity analyses will be performed based all observed data up to Day 57. The change from baseline (Day 1) to Day 57 will be analyzed using a MMRM (Section 7.6.1.3).
 - Another sensitivity analyses will be performed using MMRM with imputation of missing values for participant who discontinue treatment or who are withdrawn from the study. The imputed missing values will be adjusted using a TPA (Section 7.6.2).
- **Supportive analyses to secondary endpoint:** The secondary efficacy endpoint will also be analyzed using ANCOVA by FAS and mITT population..

The descriptive statistics for observed and change from baseline at each visit of the hardness measurements (as measured by durometer) by treatment group will be provided for participant level and nodule level.

A listing of nodular hardness by participant will be provided.

7.6.3.3.2. Nodule Level Analyses:

Nodule level analyses will be performed on observed data using MMRM (Section 7.6.1.3) and to assess the impact of missing data using MMRM of missing values for participant who discontinue treatment or who are withdrawn from the study. The imputed missing values will be adjusted using a TPA (Section 7.6.2).

The mean change in nodular hardness from Baseline to Day 57 for EN3835 compared to placebo will be analyzed using a MMRM. An unstructured covariance matrix will be used to model the covariance of within-participant values. The Kenward-Roger approximation will be used to estimate denominator degrees of freedom. If the convergent criteria are not met then other covariance matrix structure, ie., autoregressive (1) (AR (1)) will be used for model. The MMRM model will include:

- The dependent variable, the change from the Baseline to each visit (ie, change from baseline score to day 15, day 29, day 43, and day 57)
- The fixed effect, treatment group, study visit, treatment by visit interaction.
- The covariate, the Baseline Nodular Hardness at Day 1, maximum of nodule length/nodule width for the respective nodule.
- The repeated measures will be the study visit and nodules.

7.6.3.4. Other Secondary Endpoints: FFI

7.6.3.4.1. Mean Change from Baseline to Days 15, 29, 43, and 57 on the Pain Subscale

The mean change from Baseline (Day 1) to Days 15, 29, 43, and 57 on the Total Pain Subscale Score of the FFI ranging from 0 (“None”) to 4 (“Extreme”) with EN3835 vs placebo and their treatment differences will be estimated using the similar statistical model based on observed data using MMRM for the mITT population (Section 7.6.1.3).

7.6.3.4.2. Mean Change from Baseline to Days 15, 29, 43 and 57 on the FFI – Pain and Difficulty Combined Score

The mean change from Baseline (Day 1) to Days 15, 29, 43, and 57 on the Total Combined (Pain and Difficulty) Subscale Score with EN3835 vs placebo and their treatment differences will be estimated using the similar statistical model based on observed data using MMRM for the mITT population (Section 7.6.1.3).

7.6.3.5. Other Secondary Endpoints: Clinician Global Impression of Scale Change and Nodular Hardness

7.6.3.5.1. Proportion of Participants Reporting a Response on the CGIC at Day 15, 29, and 43

The proportion of participants reporting a response on the CGIC will be summarized by visit and compared between EN3835 and placebo using the mITT population. The analysis will follow the primary analysis approach in Section 7.6.3.2.

7.6.3.5.2. Mean Change from Baseline to Day 15, 29, 43 and 57 for Hardness Measurements between EN3835 and Placebo

The mean change from Baseline (Day 1) to Days 15, 29, 43, and 57 in average nodular hardness of the treated nodules by durometer measurements with EN3835 vs placebo and their treatment differences will be estimated using the similar statistical model based on observed data using MMRM for the mITT population (Section 7.6.1.3).

Refer to Section 7.6.3.3.2 for nodule level analyses.

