10.2. Populations for Analysis

For the purposes of analysis, the following populations are defined:

- The Safety Population will include all participants who receive at least 1 injection of EN3835 or placebo. All safety and immunogenicity analyses will be based on the Safety Population.
- The ITT Population will include all randomized participants. Treatment group assignment will be based on the randomized treatment. The ITT population will be used for analysis of the primary and secondary endpoints.
- The FAS Population will include all ITT participants who receive at least 1 injection of EN3835 or placebo and have at least 1 post injection FFI pain subscale measures. Treatment group assignment will be based on the randomized treatment. This population will be used for analysis of the primary and secondary endpoints.
- The mITT Population will include all ITT participants who receive at least 1 injection of EN3835 or placebo and have both baseline and at least 1 post injection FFI pain subscale measures. The treatment group assignment will be based on the randomized treatment. This population will be used for analysis of the primary, secondary, and exploratory endpoints.

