10.3.1. Efficacy Analysis

The ITT population will be the primary population for the efficacy analysis. Efficacy analyses will also be performed for the FAS and mITT populations as supportive analyses.

For the data collected at nodule level, the analyses will be performed at participant level and nodule level. The data interpretation will be based on participant level results. The nodule level results will be supportive. The details of how to map the data from nodule level to participant level will be specified in the SAP.

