5. ANALYSES POPULATIONS

The study will use the following analyses populations for data summaries and analyses.

Table 24: Analyses Populations

Population	Definition	Displays
Safety Population	The Safety Population will include all participants who receive at least 1 injection of EN3835 or placebo.	All demographic, baseline characteristics, safety and immunogenicity analyses will be summarized based on this population. Participants will be included in the safety analyses based on the actual treatment received.
Intent-to-Treat (ITT) Population	The Intent-to-Treat (ITT) Population will include all randomized participants. Treatment group assignment will be based on the randomized treatment.	The ITT population will be used for analyses of the primary and secondary endpoints.
Full Analyses Set (FAS) Population	The Full Analyses Set (FAS) Population will include all ITT participants who receive at least 1 injection of EN3835 or Placebo and have at least 1 post injection FFI pain subscale measures. Treatment group assignment will be based on the randomized treatment.	The FAS population will be used for analyses of the primary and secondary endpoints.
Modified Intent-to-Treat (mITT) Population	The modified Intent-to-Treat (mITT) Population will include all ITT participants who receive at least 1 injection of EN3835 or Placebo and have both baseline and at least one post injection FFI pain subscale measures. The treatment group assignment will be based on the randomized treatment.	This population will be used for analyses of the primary, secondary and exploratory endpoints.

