7.6. Efficacy Analyses

For the primary and key secondary efficacy endpoints, ITT Population will be the primary analysis population. Supportive efficacy analyses will also be performed using FAS and mITT Population. If the difference between FAS and mITT is no more than 5 participants, supportive analyses using FAS will not be generated. All the efficacy listing will be provided by ITT population.

For the data collected at nodule level, analyses will be performed at participant level and nodule level.

Table 27: List of Analyses Performed on All Efficacy Endpoints

Endpoint (Primary/ Secondary /Exploratory)	Endpoint	Primary analyses	Subgroup Analyses	Sensitivity Analyses	Supportive Analyses
Primary	The difference between EN3835 and placebo in the mean change from Baseline (Day 1) to Day 57 on the foot pain subscale (total score on 9 items) of the FFI ranging from 0 (“None”) to 4 (“Extreme”).	ANCOVA (ITT)	ANCOVA (ITT)	
 • MMRM based on (Observed Data) (ITT) • MMRM based on TPA (ITT) 	
 • ANCOVA (FAS) • ANCOVA (mITT)
1 st Key Secondary	The difference between EN3835 and placebo in the mean change from Baseline (Day 1) to Day 57 on the total score of the FFI pain and difficulty subscales (combined).	ANCOVA (ITT)	ANCOVA (ITT)	
 • MMRM based on (Observed Data) (ITT) • MMRM based on TPA (ITT) 	
 • ANCOVA (FAS) • ANCOVA (mITT)
2 nd Key Secondary	The difference in the proportion of EN3835-treated participants and those receiving only placebo reporting “Minimally Improved” (+1) “Much Improved” (+2) or “Very Much Improved” (+3) on the Clinician Global Impression of Change Scale, a 7-point scale ranging from –3 (“Very Much Worse”) to +3 (“Very Much Improvement”) at Day 57.	Cochran-Mantel-Haenszel method (ITT)	Cochran-Mantel-Haenszel method (ITT)	Cochran-Mantel-Haenszel based on TPA (ITT)	
 • Cochran-Mantel-Haenszel method (FAS) • Cochran-Mantel-Haenszel method (mITT)

Table 27: List of Analyses Performed on All Efficacy Endpoints (Continued)

Endpoint (Primary/ Secondary /Exploratory)	Endpoint	Primary analyses	Subgroup Analyses	Sensitivity Analyses	Supportive Analyses

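### The SAP runs the non-key by-visit secondary endpoints in mITT only, against the protocol's ITT, and leaves the non-responder rule for by-visit CGIC unsettled

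*SAP*

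**What the plan says.** **Protocol.** Section 10.3.1 is unqualified: "The ITT population will be the primary population for the efficacy analysis". It gives the other sets a secondary role: "Efficacy analyses will also be performed for the FAS and mITT populations as supportive analyses". Section 10.2 says "The ITT population will be used for analysis of the primary and secondary endpoints", and says of mITT, "This population will be used for analysis of the primary, secondary, and exploratory endpoints". The CGIC estimand in 10.3.1.2.2 targets the ITT Population, counts early discontinuation and loss to follow-up as non-response, and asks for the risk difference at each visit.

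**SAP.** Table 24 repeats the protocol: "The ITT population will be used for analyses of the primary and secondary endpoints". Section 7.6 is narrower: "For the primary and key secondary efficacy endpoints, ITT Population will be the primary analysis population". Table 27 and Sections 7.6.3.4 to 7.6.3.5 then name mITT as the only population for the remaining secondary endpoints: FFI pain, FFI pain and difficulty combined, CGIC response and nodular hardness, by visit. Under 7.6.3.5.1, by-visit CGIC response is "compared between EN3835 and placebo using the mITT population". That section adds "The analysis will follow the primary analysis approach in Section 7.6.3.2", and in 7.6.3.2 early withdrawals are non-responders; 4.8.1 has the same rule. Table 28 lists one change from protocol, on prior medications, and nothing on populations.

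**The concern.** mITT is defined partly by what happens after randomization: it needs an injection and at least one post-injection FFI pain score. Estimating a stated secondary endpoint only in that set gives up the randomized comparison that the protocol chose as primary, and does so without saying so.

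For a responder endpoint with non-responder imputation the choice has a direction. Someone removed from the set leaves the denominator; someone kept without a response stays in it as a failure. Removing early losses therefore raises the response rate in the arm that loses more. Protocol 3.2.1 reports injection-site pain, swelling and bruising as common after EN3835, so unequal early loss is conceivable.

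Table 27 also lists Day 57 CGIC twice, in ITT as key secondary endpoint 2 and in mITT in the by-visit row. The heading of 7.6.3.5.1 covers only Days 15, 29 and 43.

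**Working it through.** **1. Which participants mITT removes.** By SAP Table 24: those with no injection, no baseline FFI pain score, or no post-injection FFI pain score. The definition names no visit. The FFI is in the EOS/ET column of the Schedule of Assessments, and Protocol 8.1 and 8.2 ask for an ET visit from participants who stop early, so a participant who leaves before Day 15 but completes the ET FFI stays in mITT. Anyone who leaves after one post-injection score also stays.

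**2. Which endpoints can move.** The MMRM endpoints use observed changes from baseline. A participant with no post-baseline value contributes nothing in either population, so those results are essentially the same. CGIC response can move, because non-responder imputation gives such a participant a value in ITT.

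**3. Base numbers.** Protocol 10.1 assumes a difference of 5.0, SD 10, 85% power and 2-sided alpha 0.05. The noncentral t gives power 0.846 at 72 per arm and 0.851 at 73, so the stated 73 reproduces. 146 / (1 − 0.15) = 171.8, giving 172, or 86 per arm. The documents state no figure for by-visit CGIC.

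**4. Size if the non-responder rule governs.** Assumptions, not from the documents: ITT response 60% vs 40%, and e exclusions per arm, all non-responders. Strata are ignored.

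mITT rate = ITT rate × 86 / (86 − e)

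SE of the ITT difference = √(2 × 0.24 / 86) = 7.5 points

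| Exclusions, EN3835 vs placebo | EN3835 | Placebo | Difference (points) |
|---|---|---|---|
| 0 vs 0 (ITT) | 60.0% | 40.0% | 20.0 |
| 3 vs 3 | 51.6/83 = 62.2% | 34.4/83 = 41.4% | 20.7 |
| 4 vs 1 | 51.6/82 = 62.9% | 34.4/85 = 40.5% | 22.5 |
| 6 vs 0 | 51.6/80 = 64.5% | 34.4/86 = 40.0% | 24.5 |
| 0 vs 6 | 51.6/86 = 60.0% | 34.4/80 = 43.0% | 17.0 |

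Differences are taken before rounding. Three per arm is about a quarter of the planned dropout (0.15 × 86 = 12.9). The 6 vs 0 shift is 4.5 / 7.5 = 0.6 SE; the 3 vs 3 shift is about 0.1 SE.

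**5. A second set of assumptions.** Take 13 dropouts per arm by Day 57 and 44 vs 29 responders among 73 completers per arm.

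- ITT, non-responder rule: 44/86 − 29/86 = 51.2% − 33.7% = 17.4 points.
- mITT, non-responder rule, 2, 4 or 6 excluded per arm: 15/84 = 17.9, 15/82 = 18.3, 15/80 = 18.8 points.
- mITT, 6 excluded in one arm only: 44/80 − 29/86 = 21.3, or 44/86 − 29/80 = 14.9 points.
- Observed data only: 44/73 − 29/73 = 60.3% − 39.7% = 20.5 points, in ITT and mITT alike.

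**6. Which rule governs.** The last line matters because the SAP also points that way. Section 6.1 uses participants with non-missing values at each visit as the percentage denominator, 6.3.2 says other secondary endpoints are not imputed, and Protocol 10.5 bases non-specified secondary endpoints on observed data. Sections 4.8.1 and 7.6.3.2, invoked by 7.6.3.5.1, say the opposite for CGIC. In this example the unresolved conflict is worth about 3 points (17.4 vs 20.5), more than the population choice with balanced exclusions.

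**The case against.** The strongest reply has four parts.

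- **mITT is listed for secondary endpoints.** Protocol 10.2 and SAP Table 24 both do so. True, but Protocol 10.3.1 fixes that role as supportive, and listing mITT does not explain the absence of an ITT analysis.
- **Changing the population may change nothing.** Under SAP 6.1 and 6.3.2 a participant without a CGIC rating at a visit is outside the denominator in ITT too. This stands, and it is why changing the population flag alone is not enough.
- **Unequal early loss is not shown.** In the completed Phase 1 study no adverse event led to discontinuation of EN3835 or withdrawal (Protocol 3.2.1), and Amendment 04 lowered the assumed dropout from 20% to 15%. This stands as a caution on size. That study was open-label with 24 participants, so it does not rule out imbalance, and 6 vs 0 is a stress case.
- **Two Day 57 CGIC results are planned anyway,** because Table 27 has a supportive mITT run for key secondary endpoint 2. True; the defect is only that the by-visit row does not mark its Day 57 result as supportive.

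A reader might infer that all early dropouts disappear from the CGIC rates, or that everyone leaving before Day 15 does. The documents do not support either: one post-injection FFI pain score, including one at an ET visit, keeps a participant in mITT.

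**Conclusion.** The departure is real and undeclared: the protocol makes ITT primary for efficacy without limiting this to key endpoints, and the SAP gives the by-visit secondary endpoints in mITT only. It should be corrected, but its reach is narrow.

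Only by-visit CGIC response is materially exposed, through participants with no qualifying FFI pain score, and only if the non-responder rule governs. Under the assumed 60% vs 40% with 86 per arm, the shift is about 0.7 points for 3 vs 3 exclusions and about 4.5 points for 6 vs 0. Both the rates and the exclusion counts are assumptions. The conflict between that rule and SAP 6.1 and 6.3.2 is a second, separate gap, affecting later dropouts as well.

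A reader might also infer that a confirmatory result is at risk. It is not: Day 57 CGIC as key secondary endpoint 2 is tested in ITT with early withdrawals as non-responders, and the by-visit p-values are nominal and outside the hierarchy (SAP 6.5).

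**What to change.** 1. In SAP Table 27 and 7.6.3.4 to 7.6.3.5, make ITT the main population for the by-visit secondary endpoints and keep mITT as supportive.
2. In 7.6.3.5.1, state that for CGIC at every visit all ITT participants are in the denominator and early withdrawals count as non-responders, and that this overrides 6.1 and 6.3.2 for this endpoint.
3. Report Day 57 CGIC once as the main result (ITT, key secondary endpoint 2). Remove Day 57 from the mITT row of Table 27 or mark it supportive.

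The cost is SAP wording and a population flag, with no new data or change in sample size. CGIC response rates will be slightly lower than under mITT or observed data.
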